9.4.2.1 Estimands

The population summary measure of interest will be the odds ratio between treatment groups specified in [Section 9.4](#) for the achievement of response at the relevant time point.

Note, for PP-NRS and SD-NRS intercurrent event strategy will be applied after weekly scores at scheduled visits are calculated from daily scores.

9.4.2.2 Main Analytical Approach

Endpoints evaluated at selected visits

A generalised linear mixed effects model (GLMM) with a logit link function will be fitted using data from all visits (excluding Week 20). Treatment, visit, baseline vIGA score and the appropriate baseline questionnaire score (if different from vIGA) terms will be included in the model as fixed effects together with treatment*visit interaction.

Endpoints evaluated in periods

A generalised linear mixed effects model (GLMM) with a logit link function will be fitted using data from all periods (Weeks 1-4, 5-8, 9-12 and 13-16). Treatment, period, baseline vIGA score terms will be included in the model as fixed effects together with treatment*period interaction. The analyses will be repeated for the weeks 1-16 period dropping the terms for period and treatment*period interaction.

As described in [Section 9.2](#), any baseline covariates fitted into the primary analysis model will also be fitted in the models for these endpoints.

An unstructured covariance structure will be used. If there are issues with model convergence, other covariance structures may be considered (e.g., compound symmetry).

If responder numbers are low and there are visits/periods at which not all treatment groups have at least one response, the analysis may be modified to exclude one or more of the earlier visits/periods to ensure model convergence. For endpoints evaluated in periods, periods may be pooled in order to have more patients data in periods and ensure model convergence.

Alternatively, the mixed effects model may be replaced with an individual logistic regression models at Week 16 if this approach appears to be more appropriate for the available data. Note that if there are insufficient responders to run the model with the Week 16 visit included then no inferential analysis should be performed.

The number and percentage of responders will be reported at each visit/period together with 95% CI for the percentage of responders, calculated using the exact method for binomial proportions. At each visit/period, the adjusted odds ratio, with 95% CI and associated p-value will also be presented for each EDP1815 group (including cohorts 2+3 EDP1815 and all EDP1815 groups) compared to the pooled placebo group. For comparison between EDP1815 groups, at each visit/period, the adjusted odds ratio with 95% CI will be presented.

If the analysis is changed to exclude visits/periods, then only the summary statistics for the number of subjects with data, the number and percentage of participants with a response and the 95% CI for the percentage of responders will be shown for any visits/periods which were excluded from the model. Table footnotes will be added as appropriate to detail any changes to the planned analysis.

For Week 20 visit, only the summary statistics for the number of subjects with data, the number and percentage of participants with a response and the 95% CI for the percentage of responders will be shown.

The proportions of responders and the 95% CI will be displayed graphically. The adjusted odds ratios (with 95% CI) will be plotted by visit.

In addition, for the secondary endpoints based on the EASI, vIGA and PP-NRS only, a supportive analysis will be performed using the EDPS2.

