11.4. Planned Analyses

For all Cohort 1-3 analyses, data for the relevant endpoint will be analyzed within the same model and the Cohort 1-3 placebo groups will be pooled.

For all Cohort 4 analyses, the Cohort 4 EDP1815 data will be compared to the Cohort 4 Matched Placebo data. In separate models for the primary and selected secondary endpoints, the Cohort 1 EDP1815 data will be added to the model and compared to the Cohort 4 EDP1815 data; these analyses will be considered as exploratory.

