11.4.4. Analysis of Secondary Estimands

Continuous secondary estimands will be analyzed using a mixed model for repeated measures (MMRM) with parameters for treatment group, visit, baseline IGA score and relevant baseline score and the interaction for treatment*visit.

For the potential covariates of body mass index, gender, race and region: those covariates found to be significant in the primary analysis will be included in all models regardless of significance in order to ensure comparability of the models.

Least squares mean estimates and their 95% confidence intervals (CI) will be presented for the endpoint value at each visit. Treatment differences between each EDP1815 group and the pooled placebo group will be estimated using LS mean differences, 95% CI and p-values. Pairwise treatment differences between EDP1815 groups will be estimated with LS mean differences and 95% CI.

Least square mean (95% CI) estimates will be plotted against visit. Least square mean (95% CI) treatment differences between each EDP1815 treatment group and the pooled placebo group will also be plotted against visit.

Response estimands will be analyzed with a generalized linear mixed effects model with a logit link function. Treatment, visit, baseline IGA and the appropriate baseline questionnaire score will be included as parameters together with the treatment*visit interaction. Odds ratios with 95% CIs and p-values for each EDP1815 group compared to the relevant pooled placebo group at each visit will be presented. Odds ratios and 95% CIs will be presented for any comparisons between two EDP1815 treatment groups.

In the event that there are no responders in one of the treatment groups at a visit, data from that visit will be excluded from the model and only summary statistics will be produced showing the number and percentage of responders at that visit.

Count estimands will be analyzed with a Poisson regression model fitted with treatment and baseline IGA as covariates. An offset of log (days in study) will also be included in the model to account for any data from participants who withdrew early from the study. If the distribution of the count data suggests over-dispersion and/or zero inflation, then other models including the negative binomial or zero-inflated Poisson model may be considered.

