4.1 Pooling of Placebo Cohorts

For cohort 4 efficacy analyses, cohort 4 placebo group and set of 35 matched placebo participants from cohorts 1-3 will be pooled into a single 'cohort 4 matched placebo' group and will be used as a common control group for the cohort 4 EDP1815 treatment group.

As a sensitivity analysis, the cohort 4 EDP1815 treatment group will also be compared to the cohort 4 placebo group in all relevant analyses.

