4.4 Secondary Efficacy Analyses

The following treatment differences will be estimated:

- Cohort 4 EDP1815 vs Cohort 4 matched placebo
- Cohort 4 EDP1815 vs Cohort 4 placebo
- Cohort 4 EDP1815 vs Cohort 1 EDP1815 *

* Comparisons between cohort 4 EDP1815 and cohort 1 EDP1815 will be considered as exploratory analysis.

Treatment will consist of 4 levels (cohort 4 placebo, matched placebo from cohorts 1-3, cohort 4 EDP1815 and cohort 1 EDP1815).

The comparison with pooled placebo groups (cohort 4 matched placebo) will be done using contrasts (LSMESTIMATE statement) within the relevant SAS procedures.

For other information see the main study SAP.

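### For low-rate secondary responder endpoints the plan gives up inference at visits with an empty treatment group and has no sparse-data fallback; the Cohort 4 Addendum makes empty groups more likely by splitting the matched placebo into two model levels.

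*SAP*

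**What the plan says.** Three rules govern sparse responder data.

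- Protocol 11.4.4 is automatic: "In the event that there are no responders in one of the treatment groups at a visit, data from that visit will be excluded". Such a visit gets summary statistics only.
- SAP 9.4.2.2 is discretionary and concerns earlier visits. Where at some visit or period "not all treatment groups have at least one response, the analysis may be modified to exclude one or more of the earlier visits/periods". It also allows periods to be pooled, another covariance structure, or a stand-alone logistic regression at Week 16.
- SAP 9.4.2.2 then sets a floor: "if there are insufficient responders to run the model with the Week 16 visit included then no inferential analysis should be performed". It does not define what counts as insufficient.

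Only the number with data, the number and percentage of responders and its 95% confidence interval "will be shown for any visits/periods which were excluded from the model". There is no odds ratio and no p-value. SAP Section 13, which lists changes from the protocol, does not mention that the SAP's rule differs from the protocol's.

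For Cohort 4, Protocol 11.4 says that "the Cohort 4 EDP1815 data will be compared to the Cohort 4 Matched Placebo data", with Cohort 1 EDP1815 added only in separate models. Section 4.1 of the Cohort 4 Addendum agrees that the Cohort 4 placebo group and a "set of 35 matched placebo participants from cohorts 1-3 will be pooled into a single" group. Addendum 4.4 nevertheless specifies: "Treatment will consist of 4 levels (cohort 4 placebo, matched placebo from cohorts 1-3, cohort 4 EDP1815 and cohort 1 EDP1815"). Addendum 4.3.2 has the same four levels. The pooled placebo result is then recovered afterwards: "The comparison with pooled placebo groups (cohort 4 matched placebo) will be done using contrasts (LSMESTIMATE statement"). The Addendum's own table of changes does not list this.

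**The concern.** With no responders in a group at a visit, the maximum-likelihood odds ratio for that group is not finite. This is true in the treatment-by-visit GLMM and also in an ordinary Week 16 logistic regression, so the SAP's single-visit alternative does not solve it. The target of estimation is an odds ratio against placebo at each time point, yet whether it is estimated depends on the observed outcome. If placebo is empty and an EDP1815 arm has several responders, the data carry information that the plan does not test. Excluding the visit also removes the comparisons for arms that had responders. At Week 16 the endpoint can lose inference altogether.

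In Cohort 4 the split creates a further problem. If one placebo half is empty and the other is not, the combined placebo group has responders, but a contrast that averages the two halves on the logit scale is not finite. The comparison then fails because of the parameterisation alone.

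**Working it through.** **The plan's own figure.** Protocol 11.8 assumes 25% vs 50%, two-sided 5%, 80% power and 20% drop-out. The two-proportion formula gives 58 per group (power 80.2%), and 58/0.8 = 72.5, so 73. Both match. For Cohort 4, 56 vs 56 gives 78.8% (pooled variance) or 80.7% (unpooled), against the stated approximately 80%. The documents give no figure for the chance of an empty group.

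**Inputs.** After 20% drop-out: 75 × 0.8 = 60 per arm in Cohorts 1–3; 70 × 0.8 = 56 for Cohort 4 EDP1815; 35 × 0.8 = 28 for each placebo half. Placebo rates for the rare endpoints are not in the documents, so 2% to 10% is an assumed range.

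**Step 1. Empty pooled placebo in Cohorts 1–3.** P(zero) = (1 − p)^60.
- 2%: 0.98^60 = 0.298
- 5%: 0.95^60 = 0.046
- 10%: 0.90^60 = 0.002

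**Step 2. When an empty placebo group is informative.** Fisher exact, 0/60 against k/60: k = 5 gives p = 0.057; k = 6 gives 0.027; k = 8 gives 0.006. At least six responders are needed, so with five or fewer no significant result is lost.

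**Step 3. Share of trials losing a significant comparison**, per comparison and visit: P(zero placebo) × P(at least 6 of 60 on EDP1815).

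| Placebo vs EDP1815 | Odds ratio | P(zero placebo) | P(≥6 of 60) | Product |
|---|---|---|---|---|
| 2% vs 5.8% | 3 | 0.298 | 0.131 | 0.039 |
| 5% vs 13.6% | 3 | 0.046 | 0.844 | 0.039 |
| 10% vs 25% | 3 | 0.002 | 0.999 | 0.002 |
| 2% vs 12% | 6.7 | 0.298 | 0.741 | 0.22 |

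The odds ratio of 3 is the planning effect: (0.50/0.50)/(0.25/0.75) = 3.

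**Step 4. Cohort 4, one placebo level of 56 against two of 28.** One level: (1 − p)^56. At least one of two empty: 1 − [1 − (1 − p)^28]². Exactly one empty: 2(1 − p)^28 × [1 − (1 − p)^28].

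| Rate | One level empty | At least one of two empty | Exactly one of two empty |
|---|---|---|---|
| 2% | 32% | 81% | 49% |
| 5% | 5.7% | 42% | 36% |
| 10% | 0.3% | 10% | 10% |
| 25% | about 0 | 0.1% | 0.1% |

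The last column is the case where the pooled group has responders but the contrast still fails. With no drop-out (70 against 35 + 35), the 5% row is about 3% against 30%.

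**The case against.** A reader might infer that the SAP withdraws inference whenever any arm is empty. It does not say so. The automatic rule is the protocol's. The SAP says that earlier visits may be dropped, lists other adaptations, and reserves its no-inference sentence for a model that cannot be run with Week 16 included. That objection stands, and the difference between the two documents is itself something to reconcile.

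A reader might also infer that the losses fall mainly where the drug looks best. Rarity in any arm triggers the rule, active arms included. If all four groups in Cohorts 1–3 respond at 2%, at least one is empty in 1 − (1 − 0.298)^4 = 76% of trials, and no real signal is lost. An untested visit creates no false positive. The large loss figure also needs an assumed effect: at 2% vs 12% about three-quarters of trials with an empty placebo group would be Fisher-significant, but at the planning odds ratio of 3 and a 2% placebo rate it is 13%.

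The data stay visible, so a reader would see 0/60 against 8/60. These are secondary endpoints in a trial whose stated focus is estimation, without multiplicity adjustment, and EASI, BSA and SCORAD also have MMRM analyses. All of this limits the consequence. But an estimation-focused plan has all the more reason to report an estimate, and separate per-arm intervals are not the treatment comparison that the estimand names.

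Finally, the documents do not say whether the groups in the exclusion rule are model levels. With the four-level model the numerical failure occurs on either reading, so this does not rescue the split. The Fisher p-values above are unadjusted and do not show what a covariate-adjusted penalised model would give.

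**Conclusion.** The point holds for low-rate secondary responder endpoints, for example EASI-90, vIGA 0 and early-visit vIGA 0/1. Which endpoints have rates that low is an assumption, because the only response rates planned are 25% and 50% for EASI-50. At 25% an empty group is negligible, so the primary analysis is essentially unaffected.

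The loss in Cohorts 1–3 is modest at the planning odds ratio, about 4% of trials per comparison and visit at a placebo rate of 2% or 5%. It reaches about 22% only under a larger assumed effect. In Cohort 4 the increase in risk from the two-level placebo is large across the range and avoidable. It contradicts Protocol 11.4 and Addendum 4.1, and it is not declared as a change. These figures take the 20% drop-out as missing data; the estimand counts some withdrawals as non-response, which would move both the denominators and the rates.

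This should be changed. It does not threaten the trial's main conclusion.

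**What to change.** 1. Replace the exclusion and no-inference wording in both documents with one rule. At any visit with a zero cell, fit Firth-penalised (or exact) logistic regression at that visit with treatment, baseline vIGA and the relevant baseline score, and report the odds ratio, confidence interval and p-value. Keep the GLMM for the other visits.
2. In Cohort 4, fit the matched placebo as one treatment level for the main comparison. Put the Cohort-4-only placebo and Cohort 1 EDP1815 comparisons in separate models. The Cohort-4-only model keeps its own risk of an empty placebo group, which rule 1 covers.
3. If the four-level model is kept, align Addendum 4.1 with 4.3.2 and 4.4 and enter the departure in the Addendum's table of changes.

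The cost is SAP wording and a standard option in the planned software. The statistical price is that the estimate at those visits is single-visit and penalised, so it loses the repeated-measures handling of missing data. That is still more informative than no estimate.

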9.4.3 Count Endpoints

The following endpoints will be analysed in the same manner as described below:

- Number of courses of TCS/TCI rescue therapy
- Number of days requiring TCS/TCI rescue therapy

9.4.3.1 Estimands

The population summary measure of interest will be the rate ratio between treatment groups specified in [Section 9.4](#).

Additionally, participants with rescue therapy courses recorded in CRF but with duration of more than 8 days (adjusted for dose frequency) will be excluded from the analysis due to the potentially incorrect rescue therapy data record.

9.4.3.2 Main Analytical Approach

A Poisson regression model fitted with treatment and baseline vIGA as covariates. An offset of $\log(\text{days in study})$ will also be included in the model to account for any data from participants who withdrew early from the study. For participants who withdrew treatment early days in study will be calculated up to the end of treatment date or the end of period whichever occurs first. For

participants who completed treatment up to Week 16 days in study will be calculated up to the end of period.

In case of a greater variability among counts than expected for Poisson distribution, other models may be used (including negative binomial and zero inflated Poisson (ZIP)).

Number of courses of TCS/TCI rescue therapy endpoint will be evaluated for the following periods: Weeks 1-4, 5-8, 9-12, 13-16 and for Weeks 1-16.

Number of days requiring TCS/TCI rescue therapy endpoint will be evaluated for the following periods: Weeks 1-8, 9-16 and Weeks 1-16.

The model will be run separately for each period. Only participants with at least one visit performed in a period will be included in this period model. An offset of $\log(\text{days in the period})$ will also be included in the model based on the number of days from the first visit in the period to the last visit in the period.

Model predicted event rates and their 95% CIs will be presented for each treatment group. Rate ratios with 95% CIs and p-values for each EDP1815 group (including cohorts 2+3 EDP1815 and all EDP1815 groups) compared to the relevant pooled placebo group at each visit will be presented. Rate ratios and 95% CIs will be presented for any comparisons between two EDP1815 treatment groups. If ZIP model will be used, odds ratios for no rescue medication used and the 95% CIs will also be presented.

Number of courses of TCS/TCI rescue therapy in each period will be also plotted as histogram.

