7.2 Covariates and Subgroups

Subgroups based on baseline severity of disease will be defined as follows:

- Using baseline vIGA score of 3 for efficacy analysis
- Using baseline vIGA score other than 3 for summaries only (2, 4)

For the inferential models defined in [Section 9](#), in addition to the baseline vIGA score and relevant baseline score where applicable, the following covariates will be considered:

- Body mass index (<30 kg/m², ≥30 kg/m²)
- Sex (male, female)
- Race (Non-Hispanic white and Hispanic or Non-White)
- Region (North America, Europe, Asia Pacific)

Covariates selection will be done separately for cohorts 1-3 analyses and cohort 4.

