9.2 Selection of Additional Covariates

For all cohorts 1-3 efficacy analyses, the covariates described in [Section 7.2](#) will be considered and included in the primary efficacy model 1 described in [Section 9.3.3](#) for the primary estimand if found to be significant ($p < 0.05$). A forward stepwise selection method will be used to include the covariates after the baseline vIGA score and baseline EASI score have already been fitted.

The covariates selected for this primary model will also be used in all other analytical models including covariates.

For cohort 4 the process is described in the separate SAP Addendum.

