9.3.3 Main Analytical Approach

The primary analysis will be performed using a logistic regression model. The model will include parameters for treatment group, baseline vIGA score and baseline EASI score. As described in [Section 9.2](#) additional covariates for baseline factors will be assessed using this model for inclusion in all efficacy models. Only Week 16 data will be included in the model.

Treatment will consist of 4 levels (all placebo, cohort 1 EDP1815, cohort 2 EDP1815, cohort 3 EDP1815). Baseline vIGA will consist of 3 levels (2, 3 and 4).

The following treatment differences will be estimated:

- Cohort 1 EDP1815 vs Pooled placebo
- Cohort 2 EDP1815 vs Pooled placebo
- Cohort 3 EDP1815 vs Pooled placebo
- Cohorts 2+3 EDP1815 vs Pooled placebo*
- All EDP1815 vs Pooled placebo*
- Cohort 2 EDP1815 vs Cohort 3 EDP1815**
- Cohort 1 EDP1815 vs Cohort 2 EDP1815**

* Comparisons between pooled EDP1815 groups and pooled placebo will be considered as secondary analysis.

** Comparisons between EDP1815 treatment groups will be considered as exploratory analysis.

The comparisons between pooled EDP1815 groups* and comparisons between EDP1815 treatment groups** will be done using contrasts (LSMESTIMATE statement) within the relevant SAS procedures.

The actual and predicted probability of EASI-50 response at Week 16 in each treatment group together with the estimated odds ratios and associated confidence intervals for each treatment difference will be displayed. P-values will be displayed for the comparisons of active treatment (individual and pooled) vs pooled placebo.

Vertical bar plots for the actual and predicted probabilities of EASI-50 at Week 16 for each treatment group will be plotted.

The primary analysis approach will be repeated using the 4 supplementary estimands described in [Section 9.3.2](#).

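### The Poisson rescue-count models name baseline vIGA as their only severity covariate and leave out baseline EASI, which the trial collects and forces into its primary model

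*SAP*

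**What the plan says.** - **Count models.** SAP 9.4.3.2: "A Poisson regression model fitted with treatment and baseline vIGA as covariates", plus a log-time offset. Protocol 11.4.4 has the same terms: "Count estimands will be analyzed with a Poisson regression model fitted with treatment and baseline IGA as covariates".
- **Rescue-requirement model, by period.** SAP 9.4.2.2: "Treatment, period, baseline vIGA score terms will be included in the model as fixed effects together with treatment*period interaction". A later sentence in that section adds that "any baseline covariates fitted into the primary analysis model will also be fitted in the models for these endpoints", with a pointer to Section 9.2.
- **Primary model.** SAP 9.3.3: "The model will include parameters for treatment group, baseline vIGA score and baseline EASI score".
- **Carry-over rule.** SAP 9.2: "The covariates selected for this primary model will also be used in all other analytical models including covariates". The same section describes the selection: "A forward stepwise selection method will be used to include the covariates after the baseline vIGA score and baseline EASI score have already been fitted".
- **Candidates for selection.** SAP 7.2 lists BMI, sex, race and region, to be considered "in addition to the baseline vIGA score and relevant baseline score where applicable, the following covariates will be considered".
- **Availability of EASI.** Protocol 5.1 requires an EASI score of at least 6 at both Screening and Day 1, so the baseline value exists for eligible participants.

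**The concern.** Severity at entry is a plausible driver of rescue use. vIGA is a coarse measure of it, particularly if most participants fall in one grade. The plan indicates that they will: Protocol 11.2 and SAP 9.3.5 expect the vIGA 2 and vIGA 4 subgroups to be too small for meaningful comparison. EASI can still vary within vIGA 3, and the count models do not use that variation.

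What is at stake is some precision in the rate ratios for courses and days of rescue. There is also a risk that two programmers would fit different rescue-requirement models from the same text.

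**Working it through.** **1. Which terms enter each model**

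| Model | Severity terms named | Selected BMI, sex, race, region | Baseline EASI |
|---|---|---|---|
| Primary logistic (9.3.3) | vIGA, EASI | if selected | yes, forced |
| Rescue counts (9.4.3.2) | vIGA | yes, through 9.2 | no |
| Rescue requirement by period (9.4.2.2) | vIGA | yes | depends on reading |

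The rule in 9.2 carries over covariates that were *selected*. EASI is fitted before selection begins, so it is not one of them. Section 9.4.3.2 does not repeat the broader sentence in 9.4.2.2 about covariates fitted in the primary model. For the count models the omission is therefore clear.

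For the rescue-requirement model, the 9.4.2.2 sentence taken literally includes EASI. Taken with its pointer to 9.2, it covers only the selected extras. The carry-over text in Protocol 11.4.4 names only BMI, gender, race and region. That favours the narrow reading but does not settle the SAP wording.

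**2. How concentrated vIGA is likely to be**

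SAP Addendum 4.1.1 asks for 35 matched controls, with 5–7 mild and 3–5 severe, to match the Cohort 4 frequencies. The moderate group is then between 35 − 7 − 5 = 23 and 35 − 5 − 3 = 27, which is 66–77% of 35.

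**3. The plan's own figure**

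The only stated sample size belongs to EASI-50: 25% vs 50%, two-sided 5%, 80% power. It reproduces:

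n = [1.96·√(2·0.375·0.625) + 0.8416·√(0.25·0.75 + 0.5·0.5)]² / 0.25² = 57.7, so 58 per group; 58/0.8 = 72.5, so 73.

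No power or event rate is given for rescue, so this figure neither supports nor weakens the point.

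**4. What adding EASI could gain in the count models**

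All inputs here are assumptions except 75 per arm, which is the planned group size in Cohorts 1–3. Counts were drawn as Poisson with

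log mean = log(rate) + log(RR)·treatment + 0.3·(vIGA − 3) + b·x − b²/2,

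where x is EASI standardised within vIGA and vIGA is distributed 20/65/15%. Each scenario had 1,000 runs. The slopes b = 0.3 and 0.6 correspond to e^0.3 = 1.35-fold and e^0.6 = 1.82-fold rates per SD. The entries are the empirical SE of the log rate ratio without and with EASI; change = SE with / SE without − 1.

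| Courses per placebo participant | b | True RR | Without | With | Change |
|---|---|---|---|---|---|
| 0.4 | 0 | 1 | 0.263 | 0.264 | +0.4% |
| 0.4 | 0 | 0.6 | 0.318 | 0.319 | +0.3% |
| 0.4 | 0.3 | 1 | 0.271 | 0.268 | −1.1% |
| 0.4 | 0.3 | 0.6 | 0.309 | 0.309 | 0% |
| 0.4 | 0.6 | 1 | 0.287 | 0.270 | −5.9% |
| 0.4 | 0.6 | 0.6 | 0.337 | 0.321 | −4.7% |
| 0.8 | 0 | 1 | 0.187 | 0.188 | +0.5% |
| 0.8 | 0 | 0.6 | 0.220 | 0.221 | +0.5% |
| 0.8 | 0.3 | 1 | 0.196 | 0.193 | −1.5% |
| 0.8 | 0.3 | 0.6 | 0.222 | 0.218 | −1.8% |
| 0.8 | 0.6 | 1 | 0.218 | 0.186 | −14.7% |
| 0.8 | 0.6 | 0.6 | 0.244 | 0.221 | −9.4% |

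At a true rate ratio of 0.6 the average estimate was 0.59–0.60 with or without EASI, so there is no bias.

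At b = 0.6 the plain Poisson model without EASI also understated its own error (model SE 0.265 against 0.287 at 0.4 courses, 0.186 against 0.218 at 0.8, both at RR 1). Its type I error was 6–9%, against 4–5% with EASI. For this reason the gain does not appear as extra rejections: at RR 0.6 the rejection rate moved by only −1.5 to +0.7 points across all scenarios.

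A separate simulation used 60 per arm (75 × 0.8), a mean of 0.5 courses of 7 days, gamma heterogeneity of variance 1, robust SEs and 1,500 runs. With a 1.65-fold rate per SD the SE went from 0.352 to 0.335 (−4.8%). At 1.35-fold the fall was under 1%, and with no link the SEs were 0.323 and 0.324.

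**5. Any rescue use (logistic, single period, RR 0.6)**

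Power changed from 37.2% to 37.3% and from 58.1% to 57.8% at b = 0, from 34.8% to 35.6% and from 52.4% to 53.8% at b = 0.3, and from 30.0% to 32.4% and from 44.6% to 48.9% at b = 0.6. At b = 0.6 the average odds ratio moved from 0.56 to 0.53 and from 0.53 to 0.48. This is non-collapsibility: adjusting for EASI changes the conditional odds ratio being estimated. The simulation did not fit the repeated-period mixed model itself.

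**The case against.** The choice follows a consistent rule. The plan adjusts each model for vIGA, the stratification factor, plus the relevant baseline score where there is one. EASI is in the primary model because EASI-50 is built from it. DLQI, POEM, SCORAD and the NRS models likewise name their own baseline score and not EASI. Rescue use has no baseline score, so only vIGA is left. The protocol prespecified the count models in this form and the SAP follows it. The endpoints are secondary, the study focuses on estimation without multiplicity adjustment, and the size of any gain depends on an association the documents do not report.

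All of this stands. It shows that the omission is an orderly default and not a mistake. It does not give a reason against using a severity score already in hand, and the loss when EASI turns out to be irrelevant is immaterial.

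Two stronger readings are tempting and fail. A reader might infer that both rescue analyses adjust for three-level vIGA and nothing else. That ignores the covariates 9.2 can bring in (Addendum 4.2 does the same for Cohort 4) and the 9.4.2.2 sentence that may already include EASI. A reader might also blame the 6–9% type I error on the missing covariate. It is unmodelled over-dispersion, for which 9.4.3.2 already allows a negative binomial or zero-inflated Poisson model, although it sets no trigger for switching.

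**Conclusion.** The point holds for the count models: vIGA is their only named severity covariate, and no rule in the SAP brings in baseline EASI. Over the assumed range, adding EASI leaves the SE of the log rate ratio unchanged with no association, makes it 0–2% smaller with a weak one and about 5–15% smaller with a strong one.

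A reader might infer that the rate ratio is biased without EASI. In Cohorts 1–3 randomisation rules this out, and the simulation agrees. The argument does not extend automatically to Cohort 4, where about half the controls are non-concurrent; no calculation was made for that comparison.

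For the rescue-requirement model the documents do not establish an omission, only an ambiguity. Including EASI there adds about 0–4 points of power over the assumed range and changes the conditional odds ratio. The point is a low-cost improvement to secondary analyses and does not affect the primary conclusion.

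**What to change.** - **SAP 9.4.3.2:** add baseline EASI as a fixed covariate in every count model, in the same form as in 9.3.3, and keep it if the negative binomial or zero-inflated model is used.
- **SAP 9.4.2.2, endpoints evaluated in periods:** state whether the sentence on covariates fitted in the primary model includes baseline EASI. If it does, note that the reported odds ratio is conditional on EASI.
- **Timing:** if the relevant data are already unblinded, keep the planned count model and report the EASI-adjusted fit as a labelled sensitivity analysis.

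The cost is one covariate in the count-model text and code, one degree of freedom, and one clarifying sentence. No new data are needed.
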